7.10 STANDARD CLINICAL PRACTICE: To what extent, if any, do the planned research procedures differ from the care that people would otherwise receive at this institution or the study site if not being done locally:

The research procedure and protocol involves minimal change to standard clinical practice. The primary difference is that the intervention group would be performing the same exercises as the standard-of-care rehabilitation control group with the addition of the blood pressure cuff for blood flow restriction training applied to an occlusive pressure. For the in-person rehabilitation control group will have the cuff applied, but inflated only to 20-30 mmHg to not occlude blood flow. The International Knee Documentation Committee (IKDC) survey is not routinely administered in our orthopaedic or physical therapy clinic visits, but would be administered to both groups as a measure of patient-reported outcomes.

7.11 INSTRUMENTS: List all questionnaires, surveys, interview, or focus group guides that will be used for this study:

The International Knee Documentation Committee (IKDC) survey will be administered to patients in both study arms at 6-week, 3-month, and 6-month clinic visits or electronically.

Attach any unpublished instruments in the 'Other Study Documents' section of the Initial Review Submission Packet form after completing the study application. Published instruments should NOT be attached.

7.12 * BIOSPECIMEN COLLECTION: Are you drawing any blood or collecting other biosamples (e.g. tissue, buccal swabs, urine, saliva, hair, etc.) for analysis under this protocol and/or storage for future research: (REQUIRED)

☐ Yes ☒ No

7.13 STATISTICAL METHODS: Briefly summarize the methods and types of analyses that will be performed:

Power Analysis:

Aim 1 – Knee Extension

In a previously published study by Bowman et al., knee extension torque in this RCT's BFR group increased by 11% +/- 13 and the knee extension torque in the control group increased by 3% +/- 9 [5]. Using this data, the effect size expected is 0.72. Utilizing a goal of 0.8 power, alpha 0.05, and equal enrollment between groups, power analysis reveals a sample size goal of 50 patients (25 per group) for patients following meniscus repairs and 25 patients with additional orthopaedic knee conditions.

Aim 2 – Y-balance testing & IKDC

In Hughes et al. recent study comparing BFR to traditional heavy load resistance training in post-surgery ACL patients, Y-balance testing was most similar in the anterior direction, with scores normalized to leg length 32.9 +/- 9.7 for the BFR group and 17.5 +/- 6.7 in the traditional group [26]. Using this data, the effect size expected is 2.23. Utilizing a goal of 0.8 power, alpha 0.05, and equal enrollment between groups, power analysis reveals a sample size goal of 8 patients (4 per group) for Y-balance testing. For IKDC, overall mean difference in that paper was 35.63 +/- 7.06 for the BFR group and 23.33 +/- 8.76 for the traditional group [26]. The effect size with this data is 1.54. Utilizing a goal of 0.8 power, alpha 0.05, and equal enrollment between groups, power analysis reveals a sample size goal of 14 total patients for IKDC (7 per group). Of note, Irrgang et al. described the international knee documentation committee (IKDC) subjective knee form and determined the value for a true change in score of 9.0 points which was achieved in that study [27].

Overall, the power analysis is most limited by knee extension (75 total patients or 25 per group). To account for dropout, canceled surgeries, and patients who are unable to make all of their physical therapy visits, we aim to enroll 40% more, or a goal of **105 patients total (35 per group)**.

Statistical Analysis:

Statistical analysis will be performed comparing groups utilizing non-normative distribution analyses after obtainment of data. The alpha value for significance will be set to 0.05. Confidence intervals will be established on mean strength measures and thigh circumferences. For functional measures and IKDC survey, average scores and standard deviations will be utilized.

7.14 REFERENCES: List only the 5-10 most relevant references (a separate bibliography can be attached for reference purposes if this study involves novel approaches, agents, or an emerging technology that the IRB may not be familiar with):

Please see a full separate bibliography attached. Most relevant references are below:

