We hypothesize that quadriceps extension force will be significantly higher in patients undergoing a rehabilitative protocol with BFR versus those undergoing standard rehabilitation.

7.2 AIMS: List the specific aims:

Aim 1: Evaluate the force production and strength of the affected extremity after BFR compared to those in the standard rehabilitation control group.

Hypothesis 1: Force production, as measured by peak force determined via hand-held dynamometer at 30 and 90 degrees of knee flexion for quadriceps and hamstrings, will be significantly higher after rehabilitation with incorporation of BFR relative to patients without BFR.

We will evaluate previously described primary measures including peak quadriceps/knee extension force and limb circumferences [8-11, 16, 17]. Rating of perceived exertion (RPE) will be measured during testing to ensure the patients are meeting appropriate standards of effort (RPE goal 7-8). Measurements would be taken weekly for up to 10 weeks post-operatively during assigned physical therapy sessions; these weekly measurements will be taken by trained physical therapists at UCSF who are blinded to the patient's treatment group.

Aim 2: Compare performance on functional outcome measures relative to those in standard-of-care rehabilitative protocols and secondarily evaluate patient-reported outcomes.

Hypothesis 2: Functional outcome scores, as measured via standard scoring for single leg squat and Ybalance tests, as well as patient-reported outcomes measured via the International Knee Documentation Committee (IKDC) score will be higher in those patients undergoing BFR training relative to those undergoing standard therapy.

We will compare functional and patient-reported outcome measures between the two groups to ascertain if there are clinical outcome differences after blood flow restriction training. Functional milestones evaluated include single leg squat test, 3-hop test, and Y-balance test. Patient-reported outcomes will be measured using the IKDC standard knee evaluation form at baseline and at the conclusion of the study period. By assessing the above aims, we seek to distinguish to see if BFR training helps mitigate quadriceps atrophy in patients with orthopaedic knee conditions. This readily available and non-invasive treatment may have the potential to greatly improve orthopaedic rehabilitation and limit the detrimental effects of post-operative atrophy and progressive muscular deconditioning.

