Measurements taken by trained physical therapists at UCSF (who are blinded to the patient's assigned study group) would be taken between weekly or less frequent intervals for patients undergoing telehealth rehabilitation. These would include peak quadriceps/knee extension force and hamstring force production at 30 and 90 deg of knee flexion, measured as standard with a hand-held dynamometer which is readily available in the physical therapy center. Limb circumferences of the thigh and leg would be taken at two distances: 1/3 and 1/2 proximal along the length from the tibial tuberosity to the greater trochanter. The circumferences each would be assessed with tape measure three times for averaging.

The rehabilitation protocols themselves are standard-of-care rehabilitation, guided by the surgeon/physician and the physical therapist, and would be unchanged aside from the intervention of the BFR cuff in the intervention group. These measurements are routinely taken by the physical therapists.

Expected Outcomes: We expect to see increased strength measures and increased limb circumferences in the BFR rehabilitative protocol group relative to the standard-of-care group.

Aim 2: Compare performance on functional outcome measures relative to those in standard-of-care rehabilitative protocols and secondarily evaluate patient-reported outcomes.

Hypothesis 2: *Functional outcome scores, as measured via standard scoring for single leg squat and Y-balance tests, as well as patient-reported outcomes measured via the International Knee Documentation Committee (IKDC) score will be higher in those patients undergoing BFR training relative to those undergoing standard therapy.*

Rationale: By having a rigid physical therapy protocol with possibly increased quadricep strength secondary to BFR, we would expect better knee control and ability to complete functional testing to appropriate safe standard. Performing adequately on functional testing is critical to advise return to activity and sport. Patient-reported outcome measures are representations of patient perception, and it is important to understand patient perception of pain and function after the different rehabilitative protocols.

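### Aim 1 does not fix which force or circumference comparison is primary, at which angle and week, yet applies one unadjusted alpha of 0.05

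*Combined protocol and SAP*

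**What the plan says.** - Section 7.1 closes with a single-variable hypothesis: "We hypothesize that quadriceps extension force will be significantly higher in patients undergoing a rehabilitative protocol with BFR", compared with standard rehabilitation.
- Section 7.2, Aim 1, is broader: "We will evaluate previously described primary measures including peak quadriceps/knee extension force and limb circumferences". The list is plural and open-ended.
- Hypothesis 1 in 7.2 claims significantly higher force after rehabilitation, with force defined as "peak force determined via hand-held dynamometer at 30 and 90 degrees of knee flexion for quadriceps and hamstrings". That is two muscle groups at two angles.
- Section 7.9 places the circumferences at "1/3 and 1/2 proximal along the length from the tibial tuberosity to the greater trochanter".
- On timing, 7.2 says "Measurements would be taken weekly for up to 10 weeks post-operatively during assigned physical therapy sessions". Section 7.9 allows less frequent measurement for telehealth patients.
- Section 7.13 bases the sample size on knee extension: "Using this data, the effect size expected is 0.72", and then "Utilizing a goal of 0.8 power, alpha 0.05, and equal enrollment between groups", giving 25 per group. Section 9.3 repeats this.
- The analysis paragraph of 7.13 says "The alpha value for significance will be set to 0.05". It names no primary angle, week or cohort, no model for the repeated values, no testing order and no adjustment.

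**The concern.** A confirmatory claim needs one identified test, or a rule for combining several. Here the variable behind the sample size can be recognised, but the test cannot. Knee extension is measured at two angles and in up to ten weeks, and circumference shares the primary label. Whoever analyses the data could settle angle, week and measure after seeing the results and still be within the plan. The 5% error rate would then not apply to the headline result, and the stated power would attach to no particular comparison.

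The phrase about force after rehabilitation does not settle the time either, because the sections disagree on how long rehabilitation lasts and measurement may stop before it ends.

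**Working it through.** **1. The plan's own sample size.** Inputs from 7.13: change of 11% (SD 13) with BFR and 3% (SD 9) in controls, power 0.80, alpha 0.05, equal groups.

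Effect size = (11 − 3)/√((13² + 9²)/2) = 8/√125 = 0.716. The plan has 0.72.

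Normal approximation, n per group = 2(z_alpha + z_power)²/0.72²:
- One-sided: 2 × (1.645 + 0.842)²/0.5184 = 23.9, so 24. The t-test version gives 24.6, so 25, which matches the plan.
- Two-sided: 2 × (1.960 + 0.842)²/0.5184 = 30.3, so 31. The t-test version gives 31.3, so 32, which does not match.

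The stated 25 is therefore a one-sided calculation for one measure at one time. The plan does not state sidedness. Power from the t-test at effect size 0.72:

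| n per group | one-sided | two-sided |
|---|---|---|
| 25 | 81% | 70% |
| 35 | 91% | 84% |

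**2. Candidate measures at one time point.**
- Quadriceps at two angles: 2.
- Quadriceps and hamstrings at two angles: 2 × 2 = 4.
- The four forces plus circumference at two levels: 6. It would be 8 if thigh and leg were each measured at both levels.

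**3. Chance of at least one p < 0.05 with no true effect, tests separate and unadjusted.** If independent, this is 1 − 0.95^k. With a common correlation r between measures and two-sided tests (c = 1.96), it is

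1 − ∫ φ(u) [Φ((c − √r·u)/√(1−r)) − Φ((−c − √r·u)/√(1−r))]^k du.

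The documents give no correlations, so r is assumed.

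| k | independent | r = 0.5 | r = 0.7 | r = 0.8 |
|---|---|---|---|---|
| 2 | 9.8% | 9.1% | 8.3% | 7.8% |
| 4 | 18.5% | 15.6% | 13.0% | 11.4% |
| 6 | 26.5% | 20.7% | 16.4% | 13.9% |

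At r = 0.9 the three values are about 7%, 9% and 11%, still above 5%. Section 7.13 points to non-normal methods, so the table was also checked by simulation with 25 per group. Both t-tests and rank-sum tests came within one percentage point of it.

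**4. If every week were tested too.** This takes six measures in 10 weeks (60 tests), with the correlation between two tests set to the product of a between-measure and a between-week value. Simulation gives about 66% (0.5 and 0.7), 47% (0.7 and 0.8) and 31% (0.8 and 0.9).

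**5. When rehabilitation ends.** Set side by side:
- 7.3 and 7.9: rehabilitation lasts 8-12 weeks.
- 10.14: therapy visits run for at least six and up to twelve weeks.
- 7.2: strength is measured for up to 10 weeks, counted from surgery. Section 7.9 starts rehabilitation 3-7 days after surgery.

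A patient who stops at six weeks and one who continues to twelve have no common end-of-rehabilitation measurement, and the second has none scheduled at the end at all. No week can be assumed to be reached by everyone until these sections are reconciled.

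**The case against.** The strongest reply is that the plan does have a lead variable. Section 7.1 names quadriceps extension force alone, and 7.13 says knee extension limits the sample size. A reader might infer that the powered comparison cannot be identified at all. The documents do not support that: the variable is identifiable, and only its angle, week and cohort are open.

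Three other strong readings also fail.
- *That the plan declares six primary measures.* The sentence using the word primary names knee-extension force and circumferences. Hamstring force enters through Hypothesis 1, which does not use that word.
- *That each week is tested at 0.05.* The weekly schedule is for data collection, and Hypothesis 1 speaks of force after rehabilitation. No section plans ten weekly tests, though none excludes them.
- *That any significant result would support the force claim.* A circumference result could not. At most four measures per time point bear on Hypothesis 1.

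It can also be said that Hypothesis 1 might require all four forces to be higher, which would not inflate the error. That reading is possible, but no such rule is written, and neither is a rule that any one suffices.

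The replies narrow the point but do not remove it. Section 7.2 still gives circumference the primary label, and knee extension alone still offers two angles and several weeks.

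**Conclusion.** The concern holds as a failure to specify the primary test. If the measures are tested separately at one time point and any one may carry the claim, the false-positive chance is about 8-9% for quadriceps force at two angles, 11-16% for the four forces and 14-21% for six measures. That it exceeds 5% does not depend on the assumed correlations of 0.5-0.8, short of perfect correlation; its size does.

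The 31-66% range is a worst case that also tests every week, and should not be quoted as what the plan prescribes. The interim analysis in 13.1, which has no stated alpha rule, is not counted in any of these figures.

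**What to change.** In 7.2 and 7.13:
1. Name one primary endpoint: peak knee-extension force of the affected leg, at one stated angle and one fixed week, in the randomized meniscus-repair cohort. First reconcile the durations in 7.2, 7.3, 7.9 and 10.14, then choose a week at which all randomized patients are to be measured.
2. Estimate the group difference at that week from a repeated-measures model on the weekly values already collected. Test it once at 0.05 and state whether the test is one- or two-sided. Say how the model treats patients whose baseline comes from the uninjured leg (7.9), and how it fits with the non-normal methods in 7.13.
3. Make the other angle, hamstring force and circumferences secondary, tested by Holm or in a fixed order only if the primary test is significant. Report the other weeks descriptively.
4. Restate the power in 7.13 and 9.3 for the sidedness chosen.

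No new data are needed. The cost is that only one result can carry the confirmatory claim, and the power looks less favourable if the test is two-sided: about 70% with 25 evaluable per group, and 84% only if all 35 enrolled per group are evaluable. Reaching 80% two-sided takes 32 evaluable per group.

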7.3 DESIGN: Briefly describe the study design (e.g., observational, interventional, randomized, placebo-controlled, blinded, cross-over, cross-sectional, longitudinal, pharmacokinetic, etc.):

This study will have two parallel arms. The first one will be a **double-blinded, single-institution, randomized controlled trial** of patients undergoing in-person rehabilitation following arthroscopic meniscus repair. The second will be a **single blinded, single institution, prospective clinical trial** of patients undergoing in-person or telehealth rehabilitation of orthopaedic knee conditions. In both arms, the study compare (1) a standard-of-care rehabilitation protocol versus (2) standard-of-care rehabilitation combined with BFR training with cuff occlusion applied to the affected extremity. All patients will be enrolled prospectively, prior to beginning rehabilitation. Patients with arthroscopic meniscus repair who are unable or choose not to participate in in-person rehabilitation will be allowed to undergo telehealth rehabilitation through the second arm of this study.

Rehabilitative exercises would be advanced per the physical therapists' discretion with similar exercises for patients in both groups for direct comparison. These exercises are part of an already-established rehabilitation protocols that are in place, with the only difference being the addition of the BFR cuff in the intervention group. Patients would undergo their supervised rehabilitation for 8-12 weeks.

7.4 BACKGROUND AND SIGNIFICANCE: Briefly provide the background and significance of this study (e.g. why is this study needed) (space limit: one half page):

If this is a first in humans study, please summarize the safety data from the animal studies. For pediatric drug or device studies, please identify if this is the first study in pediatric populations.

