rehabilitation protocol versus (2) standard-of-care rehabilitation combined with BFR training with cuff occlusion applied to the affected extremity. All patients will be enrolled prospectively, prior to beginning rehabilitation. Patients with arthroscopic meniscus repair who are unable or choose not to participate in in-person rehabilitation will be allowed to undergo telehealth rehabilitation through the second arm of this study. Rehabilitative exercises would be advanced per the physical therapists' discretion with similar exercises for patients in both groups for direct comparison. For patients undergoing meniscus repairs, these standardized post-operative protocols will include a period of non-weightbearing followed by a period of weightbearing as guided by the surgeon. Intra-operatively, or prior to the initiation of the rehabilitation, the following will be noted to guide future analysis: Outerbridge Scale of Cartilage Injury, the type of meniscus tear, type of repair, and the percentage of meniscus resected. Clinical records would be reviewed for clinical, operative, and imaging data.

Aim 1: Evaluate the force production and strength of the affected extremity after BFR compared to those in the standard rehabilitation control group.

Hypothesis 1: *Force production, as measured by peak force determined via hand-held dynamometer at 30 and 90 degrees of knee flexion for quadriceps and hamstrings, will be significantly higher after rehabilitation with incorporation of BFR relative to patients without BFR.*

Rationale: If it is shown that BFR can improve strength and limit atrophy in patients with orthopaedic knee conditions, it will provide an avenue of rehabilitation for quicker recovery.

Approach:

The BFR protocol itself is guided by prior studies. While there has not been a consistent protocol used, several themes in the more recent studies remain constant and would be used. Tourniquet setting would be set to 80% of the extremity arterial limb occlusion pressure (LOP) recorded with the patient lying supine, which is similar to that of prior studies and therefore varies with a patient's personalized occlusion pressure [5, 11, 16].

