9.0 Sample Size and Eligibility Criteria

9.1 ENROLLMENT TARGET: How many people will you enroll:

105

If there are multiple participant groups, indicate how many people will be in each group:

Our goal enrollment is **105 patients total (35 per group in the randomized control trial and an additional 35 for the non-randomized group).**

9.3 SAMPLE SIZE JUSTIFICATION: Explain how and why the number of people was chosen. For multi-site studies, this is referring to the number that will be enrolled across all sites:

Power Analysis:

Aim 1 – Knee Extension

In a previously published study by Bowman et al., knee extension torque in this RCT's BFR group increased by 11% +/- 13 and the knee extension torque in the control group increased by 3% +/- 9 [5]. Using this data, the effect size expected is 0.72. Utilizing a goal of 0.8 power, alpha 0.05, and equal enrollment between groups, power analysis reveals a sample size goal of 50 patients (25 per group) for patients following meniscus repairs and 25 patients with additional orthopaedic knee conditions.

Aim 2 – Y-balance testing & IKDC

In Hughes et al. recent study comparing BFR to traditional heavy load resistance training in post-surgery ACL patients, Y-balance testing was most similar in the anterior direction, with scores normalized to leg length 32.9 +/- 9.7 for the BFR group and 17.5 +/- 6.7 in the traditional group [26]. Using this data, the effect size expected is 2.23. Utilizing a goal of 0.8 power, alpha 0.05, and equal enrollment between groups, power analysis reveals a sample size goal of 8 patients (4 per group) for Y-balance testing. For IKDC, overall mean difference in that paper was 35.63 +/- 7.06 for the BFR group and 23.33 +/- 8.76 for the traditional group [26]. The effect size with this data is 1.54. Utilizing a goal of 0.8 power, alpha 0.05, and equal enrollment between groups, power analysis reveals a sample size goal of 14 total patients for IKDC (7 per group). Of note, Irrgang et al. described the international knee documentation committee (IKDC) subjective knee form and determined the value for a true change in score of 9.0 points which was achieved in that study [27].

Overall, the power analysis is most limited by knee extension (75 total patients or 25 per group). To account for dropout, canceled surgeries, and patients who are unable to make all of their physical therapy visits, we aim to enroll 40% more, or a goal of **105 patients total (35 per group).**

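### The 0.8 power claim supports only the randomised 25 versus 25; the whole non-randomised cohort is counted as a third group of 25 although BFR and standard care are compared within it

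*Combined protocol and SAP*

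**What the plan says.** Section 7.3 (repeated in 7.9) sets up two cohorts, which it calls arms: a randomised trial after arthroscopic meniscus repair with in-person rehabilitation, and a prospective, single-blind cohort with various knee conditions treated in person or by telehealth. It then says: "In both arms, the study compare (1) a standard-of-care rehabilitation protocol versus (2) standard-of-care rehabilitation combined with BFR training". Meniscus-repair patients "who are unable or choose not to participate in in-person rehabilitation will be allowed to undergo telehealth rehabilitation through the second arm". Section 10.2 calls the second cohort non-randomised.

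Sections 7.13 and 9.3 contain one knee-extension calculation. From a published trial they take gains of 11% (SD 13) with BFR and 3% (SD 9) without, and state: "Using this data, the effect size expected is 0.72". The settings are: "Utilizing a goal of 0.8 power, alpha 0.05, and equal enrollment between groups". The result is 50 meniscus-repair patients, 25 per group, and the same sentence adds "25 patients with additional orthopaedic knee conditions". The summary reads "the power analysis is most limited by knee extension (75 total patients or 25 per group", raised by 40% to 105, or 35 per group. Section 9.1 shows what the third 35 is: "35 per group in the randomized control trial and an additional 35 for the non-randomized group".

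No split between BFR and standard care, no assignment method and no separate power is given for the second cohort. The statistical analysis paragraph in 7.13 speaks only of comparing groups. It does not say whether the cohorts are analysed separately or together.

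**The concern.** A total of 75 at 25 per group implies three groups. The design has four cells: BFR and standard care in each of two cohorts. The third 25 is therefore not a comparison group of 25. It is a cohort to be divided between two treatments, and the 0.8 power stated in the same sentence cannot carry over to the comparison inside it.

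Two things are at stake. First, a null result in the second cohort could be read as evidence of no effect because the plan appears to have powered it. Second, the hypotheses in 7.2 are worded for patients with and without BFR and are not limited to the randomised cohort, and 7.13 has no rule on separating the cohorts. An analyst could run a single test on everyone and present it as randomised evidence. That choice should be fixed before data are seen, particularly as section 13.1 plans an interim analysis.

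**Working it through.** **Inputs.** From 7.13 and 9.3: gains 11% (SD 13) and 3% (SD 9), d = 0.72, alpha 0.05, power 0.80, 25 per group randomised, 25 more in the second cohort, 40% uplift. From 9.1: 35 + 35 randomised and 35 non-randomised. Sidedness is not stated. The hypothesis in 7.1 is directional ("quadriceps extension force will be significantly higher in patients undergoing a rehabilitative protocol with BFR"), so both versions are shown. The split inside the second cohort is not stated either. A near-even split is an assumption, guided by the equal enrolment used in the calculation, and uneven splits are shown beside it.

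**Step 1: reproduce the plan's figure.**
- Pooled SD = √((13² + 9²)/2) = √125 = 11.18, and d = (11 − 3)/11.18 = 0.716, which agrees with 0.72.
- Solving the two-sample t-test (noncentral t) for 0.80 power at d = 0.72 gives 24.56 per group one-sided, so 25, and 31.27 two-sided, so 32.
- The stated 25 per group therefore reproduces with one-sided alpha 0.05 and not with two-sided.

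**Step 2: trace the third 25.** No two-group formula yields it. It enters by addition: 50 + 25 = 75 = 3 × 25. The uplift then gives 75 × 1.40 = 105, made up of 50 × 1.40 = 70 randomised and 25 × 1.40 = 35 non-randomised, which matches 9.1.

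**Step 3: power of each comparison at d = 0.72.** The noncentrality is 0.72 × √(n₁n₂/(n₁ + n₂)) with n₁ + n₂ − 2 degrees of freedom. For 12/13 this is 0.72 × √(156/25) = 0.72 × 2.498 = 1.80 on 23 df. For 25/25 it is 0.72 × √12.5 = 2.55 on 48 df.

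| Comparison | Split | Power, two-sided | Power, one-sided |
|---|---|---|---|
| Randomised, evaluable | 25/25 | 0.70 | 0.81 |
| Second cohort, 25 evaluable | 12/13 | 0.41 | 0.54 |
| Second cohort, 25 evaluable | 10/15 | 0.39 | 0.53 |
| Second cohort, 25 evaluable | 6/19 | 0.31 | 0.44 |
| Second cohort, all 35 retained | 17/18 | 0.54 | 0.67 |
| Second cohort, all 35 retained | 12/23 | 0.50 | 0.63 |

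The like-for-like contrasts are 0.41 against 0.70 (two-sided) and 0.54 against 0.81 (one-sided).

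**Step 4: what the second cohort could detect.** At 12/13, 0.80 power needs d = 1.17 two-sided or 1.03 one-sided. To reach 0.80 at d = 0.72 the cohort would need about 2 × 25 = 50 evaluable one-sided or 2 × 32 = 64 two-sided.

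The non-parametric test in 7.13 would lower all these powers slightly if the data are normal.

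**The case against.** The fair defence is that 75 and 105 are head counts, that 9.1 already separates 70 randomised from 35 non-randomised patients, and that the randomised comparison has its own calculation. All of that stands: the fault does not invalidate the randomised comparison, and 9.1 needs no change. It does not rescue 7.13 and 9.3, which attach the third 25 to the power sentence and call the sum 25 per group.

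A reader might also infer more than the documents support:

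- *That the second cohort has 0.4 power against a promised 0.8.* This mixes conventions. The 0.41 is two-sided, while the plan's 25 per group at 0.8 reproduces only one-sided. It also depends on an assumed split.
- *That the plan pools the cohorts.* It does not propose this; it is silent. A blanket ban on combining them would also rule out a stratified secondary analysis, which is defensible.
- *That the second comparison is confounded by mode and diagnosis.* That requires imbalance between treatments, and no assignment method is given. Confounding is possible, not shown. The differences that make it plausible are mixed diagnoses, self-selection into telehealth, two devices, a low-pressure control cuff described only for in-person controls, and possibly less frequent measurement by telehealth.
- *That the hypotheses should be restricted to meniscus repair.* Section 4.1 states a wider purpose. Saying where the primary test is done is enough, and the wider aim can remain.

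**Conclusion.** The point holds as a mismatch between the stated size and power and the design. The 0.8 power statement supports one comparison, the randomised 25 versus 25, and reaches 0.8 there only on a one-sided reading. The non-randomised cohort is counted as one group although two treatments are compared in it, and no calculation supports its 25.

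Under the assumed near-even split, its power at d = 0.72 is 0.41 two-sided or 0.54 one-sided with 25 evaluable. Across all the splits, retention levels and sidedness tried, it runs from 0.31 to 0.67 and never reaches 0.80. That conclusion does not depend on the exact split. The single figure does, and so should be quoted with its sidedness and assumption. All figures carry over the plan's d of 0.72 to a mixed population for which the documents give no data.

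The lack of a rule on analysing the cohorts separately is an omission to fill, not an error in the text.

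**What to change.** 1. In 7.13 and 9.3, replace the total of 75 at 25 per group, and the total of 105 at 35 per group, with: *50 evaluable (70 enrolled) in the randomised comparison, 25 evaluable per group, plus a separate non-randomised cohort of 25 evaluable (35 enrolled) that is not sized for a between-group test.*
2. State that the power claim applies only to the randomised comparison, and state its sidedness. Give the second cohort's power on the same convention: about 0.41 two-sided or 0.54 one-sided at d = 0.72, assuming a near-even split.
3. In 7.13, state that the two cohorts are analysed separately and that the primary test of the knee-extension hypothesis is in the randomised patients. State that the non-randomised comparison is exploratory, reported as estimates with 95% confidence intervals, because it may be confounded by treatment selection, diagnosis and mode. Any combined analysis should be secondary and stratified by cohort.
4. State how patients in the second cohort come to receive BFR or standard care.

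The cost is wording and the loss of a confirmatory claim from the second cohort. No extra patients are needed. If the sponsor wants a powered comparison there, the alternative is to enlarge the cohort to about 50 (one-sided) or 64 (two-sided) evaluable patients. That would not remove the possible confounding.
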